7.0 Data and Specimen Banking* N/A □

- 7.1 *Data or specimens will not be banked for future use.*
- 7.2 *Data will not be stored or associated with each specimen for future use.*
- 7.3 *Data or specimens will not be released for future use.*

8.0 Sharing of Results with Participants*

- 8.1 There are no plans to share results with study participants. If we find something of urgent medical importance, then we would like to be able to share it with the participant. This will be a very rare occurrence.
- 8.2 If the researchers are concerned about something they see on the scan they will tell the participant, and ask them if they want the

scan to be reviewed for healthcare purposes (possibly by other clinicians). They may then be referred for medical treatment. The participant and/or their insurance company may have to pay for the review for healthcare purposes, and for any such treatment.

9.0 Study Timelines*

9.1 Describe:

- The duration of an individual participant's participation in the study will be up to 3 study visits. We may also call them around 6 weeks after the visits to repeat a few questionnaires (Addiction Severity Index, SHAPS-C, COWS, NRS Pain Scale, the Subjective Units of Distress Scale, and the Visual Analogue Scale (VAS)) and see how they are doing. If they took a VNS device home then we will ask them about usage and remind them to return this to the study team.
- We expect to enroll all study participants within 2 years.
- The estimated date for the investigators to complete this study is 3/31/2025 but this depends on whether they are allowed to continue to the UH3 phase. This protocol contains details about the UG3 phase.

10.0 Inclusion and Exclusion Criteria*

10.1 Inclusion and exclusion criteria are listed below. Potential participants will be screened for eligibility by a staff member. We will try to pre-screen subjects via phone using a verbal consent and a waiver of documentation when possible. Otherwise, potential subjects will come in for a screening visit. At the first visit, study staff will confirm eligibility using a checklist.

10.2 The Inclusion and Exclusion Criteria for Study #1: Subjects aged 18 and over who: 1) meet criteria for OUDs based on DSM-5 criteria. The Inclusion and Exclusion Criteria for Study #2: Subjects aged 18 and over who: 1) meet criteria for OUDs based on DSM-5 criteria; 2) have IV access.

Exclusion Criteria: 1) positive pregnancy test; 2) meningitis; 3) moderate traumatic brain injury; 4) neurological disorder or organic mental disorder; 5) history of loss of consciousness greater than one minute; 6) current pregnancy or breastfeeding for women; 7) current or lifetime history of schizophrenia, based on the SCID; 8) a history of serious medical or neurological illness, such as cardiovascular, gastrointestinal, hepatic, renal, neurologic or other systemic illness; 9) evidence of a major medical or neurological illness that is based on the clinical judgment of the study psychiatrist; 10) carotid atherosclerosis; 11) cervical vagotomy.

PROTOCOL TITLE: Non-invasive Vagal Nerve Stimulation in Opioid Use Disorders

Several of the above exclusions will be based on the clinical judgment of the study physician. If reviewed and deemed acceptable by the study physician some exclusions may not preclude participation.

10.3 The following populations will also be excluded from the research:

- Adults unable to consent
- Individuals who are not yet adults (infants, children, teenagers)
- Pregnant women
- Prisoners

11.0 Vulnerable Populations* N/A

12.0 Local Number of Participants

12.1 Study #1 will be to optimize dosing (N=20) and Study #2 to measure brain and biological correlates of nVNS versus sham in conjunction with exposure to drug use cues (N=20).

12.2 We will ask IRB to approve 60 enrollees (total) in order to account for some screen failures. We would like to have 20 in each study to complete research procedures.

13.0 Recruitment Methods

13.1 Subjects will be recruited from newspaper advertisements, websites (like Nextdoor) and/or fliers. We may also recruit from the general outpatient population at Emory and the data warehouse. Providers may also refer patients for the study. Participants in previous research studies who have opted in for future contact might also be invited. Once a potential subject is identified, a staff member will schedule a screening interview with them to ensure eligibility with study enrollment criteria. If done via phone, a verbal consent will be obtained by the study staff member. If eligible, subject will sign study consent at first visit before starting any research related procedures. If screening is not able to be done via phone then screening for eligibility will be done in-person.

13.2 Fliers will be used describing the study inclusion criteria and a few of the procedures.

13.3 For study 1:

Compensation ranges from \$75 to a total of up to \$250 for the study. We will also pay for parking, if needed, at each clinical visit.
Visit 2: \$175 (\$75 for the MRI and \$100 for the visit)
If subjects are given a VNS device to take home, they will get an

PROTOCOL TITLE: Non-invasive Vagal Nerve Stimulation in Opioid Use Disorders

additional \$75 upon successful return of the device using a prepaid return mailer.

For study 2:

Compensation ranges from \$75 to a total of up to \$350 for the study. We will also pay for parking, if needed, at each clinical visit.

If used as a backup participant: \$50 to cover time and transportation costs

Visit 2: \$150 (PET Day)

Visit 3: \$75 (MRI Day)

If subjects are given a VNS device to take home, they will get an additional \$75 upon successful return of the device using a prepaid return mailer.

Subjects could potentially participate in both studies.

A check will be mailed to the participant after participation is completed. Sometimes this can take 3-4 weeks for Emory to approve and cut the check. Another method of payment that will be offered is using the Greenphire ClinCard system.

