- 3.2 Our preliminary data on the effects of non-invasive Vagal Nerve Stimulation (nVNS) on stress response in traumatized human subjects and patients with posttraumatic stress disorder (PTSD) show that nVNS reliably blocks peripheral sympathetic and enhances parasympathetic function, reduces inflammatory responses (interleukin-6, or IL-6), and enhances central brain responses (anterior cingulate) to stress (72). We now propose to apply this technology to the treatment of patients with OUDs. Following verification using modelling and determination of optimal dosing parameters, we will use these parameters to assess effects of nVNS versus sham stimulation on opioid craving, peripheral autonomic, cardiovascular, inflammatory, and brain functional responses measured with High-Resolution Positron Emission Tomography (HR-PET) and radiolabeled water to videos of drug cues in recently treated patients with OUDs.
- 3.3 This project will assess a new device, non-invasive Vagal Nerve Stimulation (nVNS), that does not require surgery or implantation, and that electrically stimulates the vagus nerve as it passes through the neck, dampening the sympathetic nervous system and modulating brain regions in a way that may help patients during the opioid withdrawal period and reduce relapse. Studying the effects of nVNS on opioid craving and brain and physiological responses in patients with OUDs has the potential to reduce relapse and save lives, as well as increase our knowledge of changes to the brain and physiology that underlie OUDs and successful response to treatment.

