The “VNS” group will be administered nVNS using the electroCore GammaCore-S non-invasive VNS device. The intensity of the stimulus (i.e. the current amplitude) will be adjusted by the user, to the maximum tolerable level to ensure nVNS without causing excessive pain (typically 10-30 V), the burst frequency to 5 kHz, and the envelope frequency to 25 Hz. These are the standard frequency settings that electroCore has demonstrated to be most effective in capturing the vagus nerve based on evoked potential studies. The duration of delivery will be 2 minutes, and the beginning will coincide with initiation of acquisition of the HR-PET scan which will be 90 seconds in duration; following an additional 8 minutes, a second VNS delivery will be administered, in conjunction with which another scan will be obtained. Each subject in the “SHAM” group will undergo the action of administering the intervention, but the device will be programmed such that the vagus nerve is not actually stimulated.

6.6 Procedures Performed to Lessen Probability or Magnitude of Risks:

- Psychological Assessments: There is a risk that patients may become more upset as a result of being administered questionnaires or assessments. If this occurs they will be assessed by the research coordinator and if needed [name] or one of the other study psychiatrists on the protocol. If deemed clinically appropriate they will be assessed with the Sheehan Suicidality Scale and if there is a score greater than 0 escorted to the Emergency Room for further evaluation
- Intravenous Catheters and Venipuncture: Placement of an intravenous catheter can result in infection, bruising of the skin, or a blood clot in the vein. The risk of these complications occurring will be reduced by having the procedures performed by a professional under clean conditions and using sterile procedures. Dizziness and fainting are rare risks of blood draws that will be reduced by having the subject supine. There are no long-term side effects.
- Vagal Nerve Stimulation: Stimulation of the vagus nerve may cause muscle twitching, discomfort, or pain during treatment. Hoarseness, a change in voice, or change in taste are other temporary possible consequences but

PROTOCOL TITLE: Non-invasive Vagal Nerve Stimulation in Opioid Use Disorders

these resolve when treatment is stopped. These risks will be minimized by stopping the procedure or reducing the intensity of the stimulation

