Subjects will be getting a scans (PET/MRI) for research purposes only. The research does not require the scans to be read for healthcare purposes. However, if the researchers are concerned about something they see on the scans they will tell the subject, and ask if he/she wants the scans to be reviewed for healthcare purposes (possibly by other clinicians), and he/she may then be referred for medical treatment.

- Opioid Use Related Videos. The viewing of opioid use related videos may cause some anxiety or feelings of craving for opioids. Subjects are able to stop this test at

PROTOCOL TITLE: Non-invasive Vagal Nerve Stimulation in Opioid Use Disorders

any time if they experience anxiety, excessive cravings, or other problems or are uncomfortable with the procedure.

- **VNS Testing.** Sometimes, a subject may experience hoarseness, shortness of breath, throat pain, cough, abdominal pain, headache, and/or change in voice during treatment. A tingling/pricking/twitching feeling where the device is applied is normal, but should not cause major discomfort. These effects usually stop right away once the treatment is completed. Mild skin irritation or dizziness are other possible side effects. The VNS device should not be used on patients who have any of the following conditions: an active implantable medical device, such as a pacemaker, defibrillator, cochlear implant, and other implanted electronic device; a history of significant carotid atherosclerosis; or a cervical vagotomy.
- **Reproductive Risks.** Since this research may have bad effects on a fetus and should not be done during pregnancy, it is necessary that a pregnancy test be done first, even if, to the best of the subject's knowledge, they are not pregnant now. Women of childbearing potential will take a urine pregnancy test when they arrive for their visits. If the test is positive they will not be able to participate in the study. This study may be hazardous to a breast-feeding child. Breast feeding mothers may not participate in this study.

Women who may be pregnant should not be in this study because of possible effects of radiation exposure on their unborn child. Both men who may later father children and women of childbearing potential should be aware that exposure to radiation poses a very slight risk of genetic mutation in the next generation.

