24.0 Resources Available

24.1 Describe the resources available to conduct the research:

- Subjects in this study will be patients with opioid use disorders based on DSM-5 criteria recruited from the greater Atlanta metropolitan area. We will study patients with OUDs on medication treatment. According to the Substance Abuse and Mental Health Services Administration (SAMHSA), 109,777 (4.18%) have non-medical use of prescription pain relievers, and 48,302 are estimated to have an OUD. Based on this, there is an ample population of individuals for the study.
- Recruitments for studies 1 and 2 will take place over two years.
- Emory is one of the top biomedical research institutions in the nation, ranking among the top 20 schools of medicine in NIH research funding, at \$218 million in 2008. Emory has more than 2,500 faculty members. Emory Healthcare, which includes Emory's own or affiliated clinics and hospitals, is the largest service provider in Georgia. The clinics and hospitals, with almost 3,000 inpatient beds and more than 2 million annual outpatient and emergency visits, create an exceptional environment for patient-oriented research. Emory physicians also provide a major portion of the city's indigent and public health care. It is considered to be the premier institution for cardiology and cardiac surgery care in the Southeastern United States. Atlanta has also one of the largest African American populations of any city in the U.S. and approximately 30% of all patients in Emory Healthcare hospitals and clinics are African American in origin.
- **Emory Brain Health Center and Department of Psychiatry.** The Emory Department of Psychiatry & Behavioral Sciences, chaired by [name]., is one of the most exciting and rapidly growing psychiatry departments in the U.S. today. The faculty of the department actively pursue goals of innovation in research, education and delivery of care. Emory has moved from being a primarily a clinical and regional department to one of the most rapidly expanding psychiatry departments in the country. Drs. [name], [name], [name]

PROTOCOL TITLE: Non-invasive Vagal Nerve Stimulation in Opioid Use Disorders

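### Section 13.3 lets people who had active nVNS in Study #1 enter sham-controlled Study #2; if the sham feels different, they may recognise their device, which could bias self-reported craving by an unknown amount

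*Combined protocol and SAP*

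**What the plan says.** The permission stands among the compensation terms in 13.3: "Subjects could potentially participate in both studies". No order, interval or exposure condition goes with it. The exclusion list in 10.2 ends with "10) carotid atherosclerosis; 11) cervical vagotomy" and has no entry for earlier nVNS or for Study #1 participation.

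Study #2 randomises to nVNS or sham. Section 6.2 has the Data Manager hold the blind and allocate devices with a random number generator. It does not say in so many words that participants are blinded; the sham control and the held blind imply it.

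On what participants feel, 6.5 says that intensity in the VNS group "will be adjusted by the user, to the maximum tolerable level", and 15.1 says "A tingling/pricking/twitching feeling where the device is applied is normal". For the sham, 6.5 says that "the device will be programmed such that the vagus nerve is not actually stimulated" and also refers to published methods that are not part of the documents.

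Subjective craving is part of the primary endpoint in 4.1. The VAS in 6.3 also asks how far the intervention eased craving.

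**The concern.** A person who has already felt active nVNS has a reference that a first-time participant lacks. If the sham feels different, that person is more likely to identify it, or to be confident of having the active device. Craving is reported by the participant, so belief about allocation can move the score, and the VAS item on perceived help is open to the same influence. Part of a difference in craving between the arms could then be expectancy.

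The documents plan no allocation-guess question, no stratification by prior exposure and no analysis without repeat participants. If this happened, nothing collected under the plan would show it. Blood flow, PEP and PPG amplitude do not pass through self-report and are less exposed.

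**Working it through.** **1. The plan's own figure.** Section 17.1 gives 10 per group from an effect size of 1.39, two-sided alpha 0.05 and power 0.80. For a two-sample t-test the noncentrality is 1.39 × √(10/2) = 3.108 on 18 df, and power is 0.836; with 9 per group it is 0.790. So 10 per group is reproduced. This figure concerns PET blood flow. No test, SD or target effect is given for craving. It is used below only to set the number per arm.

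**2. What has to be true, and what the documents say.**

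- *Someone takes part in both studies.* Allowed by 13.3; the number is not stated.
- *Study #1 comes first.* Section 3.2 points that way: "Following verification using modelling and determination of optimal dosing parameters, we will use these parameters to assess effects of nVNS versus sham stimulation". Section 24.1 says "Recruitments for studies 1 and 2 will take place over two years", which does not settle the order for an individual.
- *The person received active nVNS in Study #1.* Section 1.0 calls Study #1 open label, while 6.1 and 6.3 describe nVNS or sham. These need reconciling. On either reading some participants receive active nVNS; a blinded sham-controlled Study #1 would weaken the concern.
- *The sham is distinguishable by feel.* Cannot be judged from the documents.
- *Recognition changes reported craving.* Plausible for a self-report; not quantified.

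**3. Illustration only; every input is assumed.** Let f be the share of the Study #2 sham arm with active nVNS in Study #1, r the extra probability of recognising sham compared with a first-time participant, and e the shift in reported craving, in SD, among those who recognise it. If only the sham arm shifts, bias = f × r × e. The rejection rate is for no true effect, 10 per arm, two-sided t-test at 0.05, noncentrality bias × √5.

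| Assumption | Bias (SD) | Rejection rate |
|---|---|---|
| f = 0 | 0 | 5.0% |
| f = 0.1, r = 1, e = 0.2 to 0.5 | 0.02 to 0.05 | 5.02% to 5.13% |
| f = 0.25 to 0.5, r = 0.5, e = 0.2 to 0.5 | 0.025 to 0.125 | 5.03% to 5.81% |
| f = 0.25 to 0.5, r = 1, e = 0.2 to 0.5 | 0.05 to 0.25 | 5.13% to 8.27% |
| f = 0.5, r = 1, e = 0.5, opposite shifts in both arms | 2 × 0.25 = 0.5 | 18.5% |

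The formula treats the shift as uniform across the arm. Simulating exactly 5 of 10 sham participants shifted by 0.5 SD (400,000 runs) gives 7.8% rather than 8.3%, because the mixture adds variance.

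**4. Precision of an analysis without repeat participants.** The 95% CI half-width is t(0.975, 2n−2) × √(2/n). At n = 10 per arm: 2.101 × 0.447 = 0.94 SD. If half of each arm are repeat participants, n = 5: 2.306 × 0.632 = 1.46 SD.

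**5. Room for distinct participants.** Section 12.2 asks for 60 enrollees and 20 completers per study. Without overlap, 20 + 20 = 40 completers, leaving 60 − 40 = 20 (33% of 60) for screen failures and non-completers.

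**The case against.** The best defence is that harm needs every link in the chain above, and none is shown. The trigger is one permissive sentence in a payment paragraph, and 60 enrollees for 40 completers is compatible with little or no overlap. If the sham gives a matching skin sensation under the published methods that 6.5 cites, the mechanism largely disappears. First-time participants may also judge by sensation, since 15.1 describes the feeling as normal, so only the added recognition counts. The planned model and the sample size concern blood flow, and craving is an unpowered component in a small mechanistic study.

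All of this stands as a limit on size. It does not remove the point: the plan allows the situation, the outcome exposed is named in 4.1, and nothing planned would detect it.

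Stronger readings are tempting, and the documents do not support them:

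- A reader might infer that the Study #2 blind fails or that the craving result is invalid. Neither overlap nor a perceptible difference between devices is established.
- A reader might take 8.3% or 18.5% as an estimated or maximum error rate. Both come from assumed inputs and from a t-test the plan does not specify. The first is exceeded merely by letting both arms shift, and neither is a bound.
- A reader might infer long prior exposure from "If subjects are given a VNS device to take home" in 13.3. That clause is conditional, is written for both studies, and does not say whether the device is active or sham.

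**Conclusion.** The point holds as a gap in eligibility and in blinding assessment, of minor to moderate severity. Following the plan can place people with experience of active nVNS in a sham-controlled comparison of self-reported craving. The direction of concern is clear, but no magnitude can be derived: the amount of overlap, the order for each person, the feel of the sham and the effect of recognition are all unstated. With few repeat participants the effect is negligible on the inputs tried. The severity rests on the cheapness of the remedy and on craving being a named endpoint component, not on the illustrative rates. The conclusion assumes that participants in Study #2 are meant to be blinded.

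**What to change.** In 10.2 and 13.3, state that people who received active nVNS in Study #1 do not enter Study #2, and add a question on prior nVNS at screening. Section 10.2 lets the study physician set some exclusions aside, so say whether this one may be waived. If Study #1 proves to have a blinded sham arm, the Data Manager would have to apply the rule, or it could cover all Study #1 participants.

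The cost is one eligibility line, one screening question and a somewhat smaller pool. Recruitment difficulty is a ground for stopping in 18.1. The 20 spare enrollees may be enough, but no screen-failure rate is given, so that cannot be checked. Reversing the order of the studies is not a practical way out, because 3.2 places dose finding first.

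If overlap is kept, record prior nVNS exposure, ask every Study #2 participant to guess the allocation, and report craving with and without repeat participants. The guess must be collected during the study and also picks up guessing by first-time participants. Label the comparison as descriptive, given the half-widths above. This alternative costs no recruitment.

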14.0 Withdrawal of Participants*

- 14.1 The PI does not anticipate any circumstances where a participant may wish to withdraw since this study only requires a very short-term in-person participation. However, if after data collection, a participant contacts the PI wishing to not be included in any data analysis/publication, their data will be withdrawn from analysis when possible.
- 14.2 If the investigator decides to terminate a subject's participation in the research, the investigator will explain to the subject the reasons for this action and, as appropriate, other options for this participant.
- 14.3 As soon as a participant informs the PI they wish to withdraw, a notation will be made in the subject's binder and/or in Redcap. This documentation will include the date, rationale, and what components of the study for which the subject chooses to continue participation.

